### 8. STATISTICAL METHODOLOGY

# 8.1. Study Subjects

### 8.1.1. Subject Disposition

Subject disposition will be summarized on the RAND population. Subject disposition will be listed on the RAND population.

# 8.1.2. Analysis Population

Analysis populations will be summarized by treatment group. Analysis populations will be listed on the randomized population.

### 8.1.3. Number of subject screened

The number of subjects screened will be summarized and listed.

# 8.1.4. Demographic and Other Baseline Characteristics

The following demographic and other baseline characteristics will be used.

	Category	Descriptive
Age		Yes
Sex	Female	Yes
Ethnicity	Hispanic or Latino, Not Hispanic or Latino, Not Reported, Unknown	Yes
Race	American Indian or Alaska Native, Asian, Black or African American, Native Hawaiian or Other Pacific Islander, White, Not Reported, Other	Yes
Height (cm)		Yes
Weight at Day 1 (kg)		Yes
BMI (kg/m  )		Yes
Baseline nonmenstrual pelvic pain		Yes
Baseline dysmenorrhea		Yes
Baseline dyspareunia score		Yes

Usage of analgesic agents	
	Yes
Years from initial diagnosis	Yes

Demographic and other baseline characteristics will be summarized on the SAF and ITT population.

Demographic and other baseline characteristics will be listed on the RAND population. If several kinds of race are selected in the eCRF, it is treated as 'Multiple' in SDTM. Medical history will be summarized and listed on the SAF population.

# 8.1.5. Treatment Duration and Compliance

Treatment duration and compliance will be summarized on the SAF and ITT population. Treatment duration and compliance will be listed on the RAND population.

#### 8.1.6. Concomitant Medication

Concomitant medication will be summarized in table and listed on the SAF population. Prohibited medication will be listed on the SAF population.

### 8.2. Efficacy Assessments

All efficacy analyses will be performed on ITT population. All applicable endpoints are summarized.

[figure not shown]
### 8.2.1. Primary Efficacy Endpoint

[figure not shown]
Mean change from Baseline through Week 16 in nonmenstrual pelvic pain will be analyzed in table.

As the Primary analysis, Change from Baseline through Weeks 4, 8, 12, and 16 in the mean scores of nonmenstrual pelvic pain will be analyzed using a repeated measures analysis of covariance model with an unstructured covariance structure. The analysis model will include Baseline value of the endpoint and baseline value\*treatment as a covariate; weeks, treatment and weeks\*treatment as fixed effect; subjects as random effect. The Kenward-Roger approximation was used to estimate the denominator degrees of freedom. Point estimates and 95% CIs for the difference between each active dose and placebo at Week 16 and other time points will be obtained. In the event that this analysis model fail to converge, ARH(1), AR(1), CS correlation matrix will be used sequentially.

The primary efficacy analysis will be also performed on PP population.

As the secondary analysis, the primary analysis will be conducted for the primary endpoint with the last observation carried forward method for imputing the missing value at or before the Week 4, 8, 12 and 16.

[figure not shown]

Time to rescue medications is defined as the number of days from Day 1 to the first use of a rescue medication during the treatment period for patients who did not take rescue medications in the last 35 calendar days during the screening period.

Time to rescue medications will be analyzed using a log-rank test, and significance difference test based on Restricted Mean Survival Time. Same analyses will be conducted for time to hospitalization and time to surgeries.

The logistic regression model will be used to analyze the response rate (percentage) based on nonmenstrual pelvic pain . Odds ratio and risk ratios for the percentage of responders will be calculated. The analysis model will include categorization of "response" and "no response" as the dependent variable, treatment arm as the main effect, and the Baseline score for nonmenstrual pelvic pain as the covariate. This analysis will be conducted using observed case and last observation carry forward (LOCF) respectively. The last observation carried forward method will be used for the missing value at or before Week 16.

In addition, this analysis will be conducted to dysmenorrhea pain responders and dyspareunia pain responders in the same way. And, in each responder modified by analyses will be repeated in the same way.

The plot of LS mean of change from baseline value (and SE as error bar) of dysmenorrhea and dyspareunia score will be generated.

[figure not shown]
The plot of LS mean percentage change from baseline value (and SE as error bar) of dysmenorrhea and dyspareunia score will be generated.

The ROC curve of cutoff numbers for clinical responder based on nonmenstrual pelvic pain, dysmenorrhea and dyspareunia score scale will be generated.

Responder modified by analysis use analyses will also be performed by subgroups described as below. This subgroup analysis will be performed on Week 12 and Week 16 values.

Subgroup	Category
Age	$< 25, \ge 25 \ and \le 35, > 35$
Race	American Indian or Alaska Native, Asian, Black or African
	American, Native Hawaiian or Other Pacific Islander, White, Not

	Reported, Other	
Ethnicity	Hispanic or Latino, Not Hispanic or Latino, Not Reported,	
	Unknown	
Baseline pain score for	< Median of Baseline pain score for DYS	
DYS	≥ Median of Baseline pain score for DYS	
Baseline pain score for	< Median of Baseline pain score for NMPP	
NMPP	≥ Median of Baseline pain score for NMPP	
Baseline pain score for	< Median of Baseline pain score for dyspareunia	
dyspareunia	≥ Median of Baseline pain score for dyspareunia	
Baseline analgesic use		
Time since diagnosis	$< 2, \ge 2 \ and < 5, \ge 5$	

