7 STUDY DESIGN

7.1 Overall Study Design

7.1.1 Study Methodology

This is a Phase 2, randomized, double-blind, placebo-controlled study, stratified by moderate or severe pain to evaluate safety and efficacy of MT-2990 in women with endometriosis-associated moderate to severe pain. Approximately 76 subjects will be randomized into the study, with approximately 38 subjects in each treatment arm. The approximate duration of the study per subject is 52 weeks, inclusive of the Screening period, Double-blind Treatment period, and the Extended Follow-up period.

Following the Screening period, eligible subjects who have met all the eligibility criteria and have moderate or severe nonmenstrual pelvic pain, and dysmenorrhea will be randomized into the study. Approximately 38 subjects per arm will be enrolled. Subjects will be randomly allocated to 1 of 2 treatment groups (placebo or MT-2990 in a ratio of 1:1.

All efficacy and safety measures will be collected during the 16-week Double-blind Treatment period.

End-of-treatment (EOT) will occur at Week 12 (Visit 7) and primary and secondary efficacy endpoints will be assessed at the Week 16 (Visit 9) visit. Subjects who discontinue from the study will complete the procedures for Visit 9 within 10 days of discontinuation (or as soon as possible after the site becomes aware of the discontinuation).

During the Extended Follow-up period, visits will be conducted via a telephone call at Week 27 (Visit 10) and at Week 38 (Visit 11).

The Sponsor will be unblinded after Week 16 (Visit 9), while the Sites and subjects will remain blinded until the end of the Extended Follow-up period at Week 38 (Visit 11). During the study, database will be locked twice: at Week 16 (Visit 9) to assess safety and efficacy, and at Week 38 (Visit 11) to assess other outcomes during the Extended Follow-up period.

There will be 3 interim assessments for safety. The first interim assessment for safety will be performed when 20 subjects are randomized and have completed the Week 2 visit. The second interim assessment for safety will be performed when 50% of the subjects are randomized and have completed the Week 4 visit. The third interim assessment for safety will be performed when 50% of the subjects are randomized and have completed the Week 16 visit.

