14 STATISTICAL METHODS AND PLANNED ANALYSES

14.1 Determination of Sample Size

Power analysis for sample size calculation was performed under 2-sample t-test at the 5% level of significance to identify significance of the difference between MT-2990 and placebo on the mean change from Baseline to Week 16 in nonmenstrual pelvic pain. A total of 28 subjects per arm will provide at least 80% power for detecting a clinically meaningful difference (placebo versus treatment) of -0.5 in the mean change from Baseline in nonmenstrual pelvic pain and a standard deviation (SD) of 0.65, based on results from the effect of As this study is exploratory study (proof of concept study), multiplicity for multi-endpoint is not considered. Assuming a drop-out rate of 25%, a total of 76 subjects (38 subjects per arm) are planned to be randomized in this study.

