14.3.4 Analysis Method

14.3.4.1 Primary Analysis

Change from Baseline to Weeks 4, 8, 12, and 16 in the monthly mean scores of nonmenstrual pelvic pain will be analyzed using a repeated measures analysis of covariance model with an unstructured covariance structure. The analysis model will include Baseline value of the endpoint as a covariate; weeks and treatment as fixed effect; subjects as random effect. Point estimates and 95% CIs for the difference between each active dose and placebo at Week 16 and other time points will be obtained.

[figure not shown]

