14.3.4.2 Secondary Analysis

Similar analysis to the primary analysis will be conducted for the primary endpoint using the last observation carried forward method for the missing value at or before the Week 16 visit

Similar analysis to the primary endpoint will be conducted to the key secondary endpoints.

Similar analysis to the primary analysis will be conducted for the secondary endpoints that will reported as numeric data.

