### 3. STUDY DESIGN

# 3.1. Study Design

This is a Phase 2, randomized, double-blind, placebo-controlled study, stratified by moderate or severe pain to evaluate safety and efficacy of MT-2990 in women with endometriosis-associated moderate to severe pain.

Following the Screening period, eligible subjects who have met all the eligibility criteria and have moderate or severe nonmenstrual pelvic pain, and dysmenorrhea will be randomized into the study. Approximately 38 subjects per arm will be enrolled. Subjects will be randomly allocated to 1 of 2 treatment groups (placebo or MT-2990) in a ratio of 1:1. A single

dose of placebo or

End-of-treatment (EOT) will occur at Week 12 (Visit 7) and primary and secondary efficacy endpoints will be assessed at the Week 16 (Visit 9) visit. Subjects who discontinue from the study will complete the procedures for Visit 9 within 10 days of discontinuation (or as soon as possible after the site becomes aware of the discontinuation).

During the Extended Follow-up period, visits will be conducted via a telephone call at Week 27 (Visit 10) and at Week 38 (Visit 11). Visit 11 will be the end of study (EOS) visit.

The Sponsor will be unblinded after Week 16 (Visit 9), while the Sites and subjects will remain blinded until the end of the Extended Follow-up period at Week 38 (Visit 11). During the study, database will be locked twice; Week 16 (Visit 9) to assess safety and efficacy, and at Week 38 (Visit 11) to assess other outcomes during the Extended Follow-up period.

The study design schema is presented in.

[figure not shown]
[figure not shown]
[figure not shown]
[figure not shown]

Figure 1 Study design schema

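### The randomization is stratified by moderate or severe pain, but neither the primary model nor the responder model includes the stratum; the likely loss is small and conditional

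*SAP*

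**What the plan says.** SAP 3.1 calls the trial a "placebo-controlled study, stratified by moderate or severe pain", and Protocol 7.1.1 likewise has it "stratified by moderate or severe pain". Allocation is 1:1.

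For the primary endpoint, SAP 8.2.1 states: "The analysis model will include Baseline value of the endpoint and baseline value" by treatment as covariates, with weeks, treatment and weeks by treatment as fixed effects and subject as random. Protocol 14.3.4.1 has a shorter list: baseline, then "weeks and treatment as fixed effect; subjects as random effect". SAP section 1 gives the SAP precedence on analysis, and SAP section 10 (changes from the protocol) does not mention the stratum.

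The logistic responder model in SAP 8.2.1 uses "treatment arm as the main effect, and the Baseline score for nonmenstrual pelvic pain as the covariate". The SAP then says that "this analysis will be conducted to dysmenorrhea pain responders and dyspareunia pain responders in the same way". Protocol 14.3.4.2 carries the repeated-measures model forward: "Similar analysis to the primary endpoint will be conducted to the key secondary endpoints".

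On sample size, Protocol 14.1 says: "Power analysis for sample size calculation was performed under 2-sample t-test", with 28 per arm for at least 80% power, a difference of -0.5, an SD of 0.65 and 25% drop-out, giving 38 per arm. SAP 3.3 repeats these figures.

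**The concern.** Stratified randomization balances the arms on the stratum, so the true variance of the treatment estimate is reduced if the stratum is prognostic. A linear model without the stratum leaves that variation in the residual. It therefore reports a standard error that is too large, with a test below its nominal 5% level and an interval that is too wide. The estimate itself is not biased. In a logistic model the effect differs: omitting a prognostic factor moves the odds ratio towards 1 and makes the standard error smaller, with a small net loss of power.

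The continuous baseline score may already carry what the stratum carries. The readable text does not show which pain score or cut-off defines the stratum. Text is withheld around Protocol 11.4.1, so this is not a fault in the plan, but it makes the size of the loss conditional. Two things mean an exact cut of baseline cannot be taken for granted:

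- Each repeated-measures model adjusts for the baseline of its own endpoint. A stratum built on one pain score is not a cut of the covariate in the model for another.
- The analysis baseline is the average of the last 35 screening days (SAP 7.1.2.1), and nothing readable says the stratum uses that window.

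**Working it through.** **1. The plan's own figure.** Two-sample t-test, two-sided 5%, 28 per arm, difference 0.5, SD 0.65:

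- SE = 0.65 × √(2/28) = 0.174; non-centrality = 0.5/0.174 = 2.88 on 54 df.
- Power = 80.7% (27 per arm gives 79.2%).
- 28/0.75 = 37.3, rounded up to 38 per arm, 76 in total.

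The stated figures reproduce. They use no covariate, so omitting the stratum does not change them.

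**2. Closed-form check, linear model.** Let R² be the share of the model's residual variance that the stratum explains beyond baseline. It is assumed, since the documents give no value. Take arms balanced within strata and a single time point at Week 16.

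- Reported SE without the stratum: 0.174. True SE: 0.174 × √(1−R²). The ratio is 1/√(1−R²).
- True type I error without the stratum: 2 × P(T₅₄ > 2.005/√(1−R²)).
- Power without: Φ[(0.5 − 2.005 × 0.174)/true SE]. Power with: non-central t on 53 df at 0.5/true SE.

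| Assumed R² | SE too large by | True type I error | Power without | Power with |
|---|---|---|---|---|
| 0 | 0% | 5.0% | 80.9% | 80.7% |
| 0.02 | 1.0% | 4.8% | 81.1% | 81.4% |
| 0.05 | 2.6% | 4.5% | 81.5% | 82.6% |
| 0.10 | 5.4% | 3.9% | 82.1% | 84.6% |
| 0.20 | 11.8% | 2.9% | 83.6% | 88.5% |

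The column without the stratum uses a normal approximation, which accounts for part of the 0.2-point gap in the first row.

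**3. Simulation, linear model.** Week 16 ANCOVA with treatment, centred baseline and baseline by treatment, fitted with and without the stratum; 28 per arm; 8,000 replicates per cell. Assumptions not in the documents: strata 50/50 or 70/30, permuted blocks of 4 within stratum, baseline-to-change correlation 0 or 0.4, and a stratum that is either a cut of baseline or a cut of a latent score correlated 0.6 with it. The ranges span these settings.

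- Stratum is a cut of baseline: power is 0.3 to 0.7 points higher without it (SE 0.174 without, 0.175 with).
- Correlated with baseline but adding nothing: within 0.4 points either way.
- Explains 5% of residual variance: type I error without it 4.5 to 4.7%, SE 2.5% larger, power 0.9 to 1.6 points lower.
- Explains 10%: type I error 4.0 to 4.4%, SE 5% larger, power 2.3 to 3.5 points lower.

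**4. Simulation, logistic responder model.** 56 evaluable, 50/50 strata, 8,000 replicates per cell. Assumed placebo response about 30%, conditional log odds ratio 1.5, and baseline log odds ratio 0.5 per SD. Log odds ratios and SEs are medians.

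| Latent variance explained by stratum (assumed) | Log OR without / with | SE without / with | Power without / with |
|---|---|---|---|
| 0% | 1.58 / 1.61 | 0.61 / 0.62 | 75.4 / 75.5% |
| 5% | 1.51 / 1.61 | 0.61 / 0.64 | 71.6 / 73.3% |
| 10% | 1.43 / 1.61 | 0.60 / 0.66 | 67.4 / 70.4% |

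A separate large-sample fit with an assumed log odds ratio of 1.0 gave attenuation of about 1%, 3 to 4% and 6 to 10% for stratum log odds ratios of 0.5, 1.0 and 1.5. The expected z at 76 subjects changed by 0.01 to 0.07.

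**The case against.** The strongest reply is that nothing has gone wrong. The trial is declared exploratory, planned power does not depend on the stratum, any error in the linear test is conservative, and the primary model already adjusts for continuous baseline pain. If the stratum is a cut of nonmenstrual pelvic pain, which is a natural reading of the eligibility text, adding it to the primary model gains nothing and costs a fraction of a point. Every non-zero loss rests on an assumed variance share. The definition of the stratum, or a sensitivity model that uses it, could lie in withheld text.

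Most of this stands, and it is why the point is minor. Two parts of the reply on size need an answer:

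- **Drop-out.** The simulations above use intact blocks of 56. With 76 randomized and 20 lost at random, one check put type I error without the stratum at 4.9% (5% share) and 4.4% (10% share), so the conservatism may be milder than shown. A further check with the same drop-out still found about 1.5 and 3 points of power forgone.
- **Logistic model.** The shift in the odds ratio is non-collapsibility: the two models estimate different conditional odds ratios, so the shift is not bias in the SAP's estimate. In the small-sample table, the medians without the stratum are in fact nearer the assumed 1.5. The relevant comparison is power, which differs by 0.1, 1.7 and 3.0 points.

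The reply does not show the stratum in any model. Both model sentences in SAP 8.2.1 list their terms without it.

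**Conclusion.** The concern holds, as a minor one. The trial is stratified by pain severity, and the stated primary and responder models leave the stratum out. The loss is zero if the stratum is a cut of the baseline score already in the model. It is roughly 1 to 1.5 points of power if the stratum explains 5% of residual variance beyond that score, and roughly 2.5 to 3.5 points at 10%, with a slightly conservative linear test. These shares are assumptions, and the linear results approximate the Week 16 contrast of a four-visit model by a single-visit one. Planned power and the validity of the primary conclusion are not in question. What is forgone is a gain in precision that the randomization already makes available.

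**What to change.** Add the randomization stratum (moderate or severe, as recorded in the IWRS) as a two-level fixed effect in:

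- the primary repeated-measures model and its per-protocol and LOCF repeats;
- the parallel repeated-measures models for the key secondary and other numeric secondary endpoints;
- the logistic responder models for nonmenstrual pelvic pain, dysmenorrhea and dyspareunia.

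If the sponsor prefers to leave it out of a model because it is an exact cut of that model's baseline covariate, one sentence in SAP 8.2.1 saying so would settle the matter there. Either change should be made before the Week 16 database lock. The cost is one model term and one degree of freedom, at most about 0.7 points of power in these simulations if the stratum adds nothing. No new data are needed.

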### 1. INTRODUCTION

This statistical analysis plan (SAP) is based on the protocol amendment 4 dated 04 Mar. 2020. The plan covers statistical analysis, tabulations and listings of the study.

Any statistical analysis details described in this document supersede any description of statistical analysis in the protocol.

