# 3.3. Determination of Sample Size

Power analysis for sample size calculation was performed under 2-sample t-test at the 5% level of significance to identify significance of the difference between MT-2990 and placebo on the mean change from Baseline through Week 16 in nonmenstrual pelvic pain. A total of 28 subjects per arm will provide at least 80% power for detecting a clinically meaningful difference (placebo versus treatment) of -0.5 in the mean change from Baseline in nonmenstrual pelvic pain and a standard deviation (SD) of 0.65,

As this study is exploratory study (proof of concept study), multiplicity for multi-endpoint is not considered. Assuming a drop-out rate of 25%, a total of 76 subjects (38 subjects per arm) are planned to be randomized in this study.

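### The primary repeated-measures model has no baseline-by-week term, so the Week 16 difference can be modestly biased if the baseline slope drifts and score-related drop-out differs by arm

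*SAP*

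**What the plan says.** SAP 8.2.1 specifies a "repeated measures analysis of covariance model with an unstructured covariance structure". Its terms start with "The analysis model will include Baseline value of the endpoint and baseline value", and after the interaction sign continue "treatment as a covariate; weeks, treatment and weeks", closing with the weeks-by-treatment interaction and subject as a random effect. The mean model therefore contains baseline, baseline-by-treatment, weeks, treatment and weeks-by-treatment. The list is a complete sentence, so redaction does not explain the absence of baseline-by-week.

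The reported contrast is given by: "Point estimates and 95% CIs for the difference between each active dose and placebo at Week 16 and other time points will be obtained".

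Protocol 14.3.4.1 is sparser: "The analysis model will include Baseline value of the endpoint as a covariate; weeks and treatment as fixed effect; subjects as random effect". It has no baseline-by-week term either. The SAP governs, since it states: "Any statistical analysis details described in this document supersede any description of statistical analysis in the protocol".

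The model is reused. SAP 8.2.1 repeats it in the per-protocol population and, as a secondary analysis, says that "the primary analysis will be conducted for the primary endpoint with the last observation carried forward method for imputing the missing value". Protocol 14.3.4.2 applies a similar analysis to the key secondary and numeric secondary endpoints. SAP 3.3 plans for missing data: "Assuming a drop-out rate of 25"%.

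**The concern.** A likelihood repeated-measures analysis gives valid estimates when drop-out depends only on observed data, provided that its model, including the mean model, is correctly specified. This mean model lets the treatment effect vary by week but holds the baseline slope fixed over weeks. An unstructured covariance does not relax that restriction.

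The slope of change on baseline is r × SD(week)/SD(baseline) − 1, where r is the correlation with baseline. Drift is plausible. Baseline averages the last 35 days of screening (SAP 7.1.2.1), the Week 4 window follows directly, and the Week 16 window falls about three months later (SAP 7.3). Drop-out that differs by arm is plausible too: persisting pain may act mainly on placebo, and the hypersensitivity withdrawals in protocol 8.5 mainly on MT-2990.

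If both occur, part of the difference in baseline between the women remaining in each arm is carried into the Week 16 contrast. The per-protocol and LOCF analyses would not expose this, because they keep the same restriction.

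**Working it through.** **1. The plan's own figure.** Inputs from SAP 3.3: difference 0.5, SD 0.65, two-sided 5%, 80% power, 25% drop-out.
- Normal approximation: n = 2 × (1.960 + 0.842)² × 0.65² / 0.5² ≈ 26.5, so 27 per arm.
- Exact t-test power is 79.2% at 27 and 80.7% at 28, so 28 per arm is right.
- 28 / (1 − 0.25) = 37.3, so 38 per arm and 76 in total. The figure reproduces.

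**2. When the slope drifts.** With equal SDs, r = 0.70 gives a slope of −0.30 and r = 0.50 gives −0.50. With r = 0.50 and an SD ratio of 1.4, the slope is 0.50 × 1.4 − 1 = −0.30, so there is no drift. Falling correlation alone does not settle the question.

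**3. Simulation A (assumed inputs).** 76 women, true effect 0, 25% drop-out, correlation with baseline 0.65-0.78 at Week 4 falling to 0.42-0.52 at Week 16, 2,500 runs per setting, Monte Carlo SE about 0.005. Bias is in SDs of a monthly score. It is converted to points by 0.65 / SD of simulated change, where that SD is 0.98-1.08.
- Placebo women with more observed pain leave more often: 0.023-0.041 SD. In points, 0.023 × 0.65/1.08 = 0.014 to 0.041 × 0.65/0.98 = 0.027, which is 3-5% of 0.5, in favour of MT-2990. With baseline-by-week: at most 0.006 SD.
- Baseline-driven drop-out in opposite directions by arm: 0.084-0.094 SD, or 0.051-0.062 points, 10-12% of 0.5. With the term: at most 0.008 SD.
- Random drop-out: no bias; variance without the term is 0-5% larger.

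**4. Simulation B (different assumed inputs).** Baseline SD 0.5, residual SD 0.6, lag-1 correlation 0.7, true Week 16 effect −0.5, 100,000 per arm. Baseline-by-treatment stays in both fits, and the difference is read at the mean baseline. Entries are Week 16 bias in points without / with baseline-by-week; negative favours MT-2990.

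| Drop-out (placebo / MT-2990) | Slope constant −0.3 | Slope −0.2 to −0.4 | Slope −0.1 to −0.6 |
|---|---|---|---|
| Baseline-driven, same in both arms (25% / 25%) | −0.003 / −0.003 | −0.003 / −0.003 | 0.002 / 0.001 |
| Last observed score in placebo, random in MT-2990 (28% / 24%) | 0.001 / 0.001 | −0.005 / 0.005 | −0.025 / 0.000 |
| Baseline-driven in placebo only (28% / 23%) | 0.001 / 0.001 | −0.013 / 0.003 | −0.039 / 0.001 |
| Baseline-driven in both, unequal rates (38% / 14%) | 0.005 / 0.005 | −0.014 / 0.001 | −0.037 / 0.000 |
| Baseline-driven, opposite directions (24% / 24%) | 0.004 / 0.003 | −0.028 / 0.000 | −0.067 / 0.001 |

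Against 0.5, the last column is 0.025 = 5%, 0.039 = 8%, 0.037 = 7% and 0.067 = 13%.

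**5. At trial size.** Simulation B with 38 per arm, no true effect and 1,500 trials per setting, for three of the drop-out patterns (same in both arms, placebo only, opposite directions). The SD of the estimate was 0.151-0.161 without the term and 0.146-0.160 with it. In the extreme setting, mean bias was −0.064 against 0.005 and type I error about 7.3% against 4.9%. In the other settings type I error was 5.1-6.5% without the term and 4.4-6.1% with it. These fits used maximum likelihood rather than the planned Kenward-Roger method, so the error rates are approximate.

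**6. Scale against noise.** 0.027 / 0.16 = 0.17 standard errors in Simulation A's placebo case; 0.067 / 0.16 = 0.42 in the extreme case.

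**The case against.** A reader might infer that a common slope is simply wrong at Week 16, and that the model therefore no longer handles drop-out that depends on observed data. The documents do not support that. They give no baseline correlation and no visit-specific SD. Because only women with moderate or severe pain enter, baseline spread may be restricted and follow-up spread wider, in which case step 2 shows that the slope can stay flat. Nor do they give drop-out by arm, only a flat 25%. Both conditions are needed together, and neither is established. This part of the objection stands and limits the point to a conditional one.

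It is also fair that the ordinary shift is under 0.2 standard errors, that the 10-13% figure needs drop-out in opposite directions by arm, and that this is a proof-of-concept study.

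A second tempting step is to delete baseline-by-treatment. Simulation B kept that term and still removed the bias, so deletion is not needed for this purpose. No scenario tested a real baseline-by-treatment effect. Because of that term the difference depends on the baseline value at which it is read, but stating the value deals with this.

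Finally, the efficacy part of the SAP's missing-data section is not visible, so further sensitivity analyses may exist. That does not alter the stated primary model.

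**Conclusion.** The point holds in conditional form. The baseline-by-week term is absent from both documents. Two simulations with different inputs agree that its absence can bias the Week 16 difference when a drifting slope meets score-related drop-out that differs by arm, and that adding it removes the bias to within simulation error (at most 0.008). All sizes rest on assumed correlations, slopes and drop-out patterns. With milder drift (−0.2 to −0.4), the placebo score-driven case could not be told from simulation error. This is a cheap improvement to the primary analysis. It is not a flaw that endangers the trial, and it does not affect the sample size.

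**What to change.** In SAP 8.2.1, add `baseline value*weeks` to the primary model and keep weeks-by-treatment. Carry the term into the per-protocol and LOCF versions and into the key secondary and numeric secondary endpoints that are analysed similarly. Report the Week 16 LS-mean difference as the primary result. If baseline-by-treatment is kept, state that the difference is read at the overall mean baseline.

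Cost: with four visits, three extra mean parameters (from 10 to 13). The unstructured covariance is unchanged, the change in precision is negligible, and the planned 76 stands. It needs one phrase in the SAP and one line of code, made before database lock.
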